## B.2. STUDY OBJECTIVES

The ***primary objective*** of this study is to characterize the application of DTM SCS programming as a treatment for reducing intractable chronic pain of the upper limbs.

The ***secondary objectives*** of this study are to further characterize the effectiveness of DTM SCS programming for the treatment of chronic pain of the upper limbs and to collect safety data of DTM SCS programming.

## B.3. SELECTION OF STUDY POPULATION

### **B.3.1. STUDY POPULATION**

The intended study population is individuals who have been diagnosed with chronic, intractable pain of the upper limbs associated with a number of conditions, and who the Principal Investigator deems is an appropriate candidate for SCS therapy as required for this study in this Clinical Study Plan.

### **B.3.2. INCLUSION CRITERIA**

In order to participate in the study, a subject must **MEET ALL** of the following inclusion criteria:

1. Be diagnosed with chronic, intractable pain of the upper limbs related to the cervical spine and/or neuropathic arm pain.
2. Be a candidate for SCS system (trial and implant) per labeled indication (upper limb pain due to one of the conditions listed in indications statement)
3. Considering daily activity and rest, has average upper limb pain intensity of  $\geq 5$  out of 10 cm on the Visual Analog Scale (VAS) at enrollment
4. Be willing and capable of giving written informed consent to participate in this clinical study based on voluntary agreement after a thorough explanation of the subject's participation has been provided.
5. Be willing and capable of subjective evaluation, read and understand written questionnaires, and read, understand and sign the written informed consent.
6. Be 18 years of age or older at the time of enrollment
7. Be on a stable pain medication regime, as determined by the study Investigator, for at least 30 days prior to enrolling in this study
8. Be willing and able to comply with study-related requirements, procedures, and visits, including not increasing pain medications through the three months visit
9. Has adequate cognitive ability to use a patient programmer and recharger as determined by the Investigator

### **B.3.3. EXCLUSION CRITERIA**

In order to participate in the study, a subject must **NOT MEET ANY** of the following exclusion criteria:

1. Has a medical, anatomical, and/or psychosocial condition that is contraindicated for commercially available Intellis™ SCS systems as determined by the Investigator
2. Have a medical condition or pain in other area(s), not intended to be treated with SCS, that could interfere with study procedures, as determined by the Investigator
3. Currently enrolled or planning to enroll in an interventional clinical study that could potentially confound the study results (co-enrollment in an interventional

study is only allowed when documented pre-approval is obtained from the study manager or designee)

4. Has an existing active implanted device such as a pacemaker, another SCS unit, peripheral nerve stimulator, and/or drug delivery pump.
5. Has pain in other area(s) and/or medical condition requiring the regular use of significant pain medications that could interfere with accurate pain reporting, study procedures, and/or confound evaluation of study endpoints, as determined by the Investigator
6. Has significant cervical stenosis, as determined by the Investigator
7. Has facet spondylosis, as determined by the Investigator
8. Has mechanical spine instability, as determined by the Investigator
9. Has undergone, within 30 days prior to enrollment, an interventional procedure and/or surgery to treat upper limb pain, which is providing significant pain relief
10. Has unresolved major issues of secondary gain (e.g., social, financial, legal, such as worker compensation matters)
11. Be pregnant as determined by urine testing unless female subject is surgically sterile or post-menopausal. If female, sexually active, and childbearing age, subject must be willing to use a reliable form of birth control.
12. Have evidence of an active disruptive psychological or psychiatric disorder as determined by a psychologist
13. Have a current diagnosis of a progressive neurological disease as determined by the Investigator
14. Have a current diagnosis of a coagulation disorder, bleeding diathesis, progressive peripheral vascular disease or uncontrolled diabetes mellitus
15. Have a condition that the Investigator determines would significantly increase perioperative risk
16. Any previous history of surgery on the posterior elements (laminectomy, posterior fusion) of the cervical spine
17. Have metastatic malignant disease or active local malignant disease
18. Have a life expectancy of less than 1 year
19. Have an active systemic or local infection
20. Have within 6 months of enrollment a significant untreated addiction to dependency producing medications or have been a substance abuser (including alcohol and illicit drugs)

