### **B.6.3. ELIGIBILITY CRITERIA EVALUATION**

The eligibility of subjects who have consented participation will be assessed based on the inclusion and exclusion criteria. Study subjects must meet all of the study inclusion criteria and none of the study exclusion criteria to be eligible. Assessments for eligibility include average pain intensity (which will be used as Baseline pain intensity), other pain intensity (such as secondary pain or related pain), medication usage, medical records and history, and the Investigator's clinical judgment. Subjects with confirmed eligibility will proceed to Baseline assessment, while subjects who do not will be considered screen failures and discontinued from the study.

**Figure 1.** A flowchart of the study.

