#### **B.6.15 OTHER ASSESSMENTS AND INFORMATION**

At any time during the study, if lead migration is suspected, the subject may have additional AP and lateral X-rays taken to confirm the new lead position in order to aid the Investigator in determining a course of action.

Paresthesia testing may also be performed to assess lead location and therapy coverage of pain areas. Programming adjustments may be made based on patient feedback following assessment.

Additional information on Medication Usage:

- The Investigator will instruct all subjects to take the Baseline doses of pain medication until the 3-Month Visit. However, after Device Activation Visit, the Investigator may reduce the dose of pain medication if the subject is benefitting greatly from DTM SCS therapy and not benefitting from Baseline dose pain medication.
  - Subjects should not fluctuate medication usage nor dosages even if the dose is at or below Baseline doses. The Investigator/Study staff will instruct all subjects to maintain stable dosing of medication for at least two weeks prior to scheduled follow-up visits.
- Following trial and permanent implants, the clinical site's standard practice for prophylactic pre-surgery antibiotics and post-surgery pain medications will be followed. Investigators/Study staff will instruct subjects not to change usage of any other concomitant pain medications.

Remote data collection from the subjects is allowed. This should be evaluated on a case by case basis, pending Investigator's approval based on safety and clinical condition. Subjects who are not demonstrating study compliance, e.g. not returning phone calls, not charging device or turning the device off should not be mailed study questionnaires until they demonstrate compliance with the study. The site should continue to contact the subject and ensure compliance before mailing the questionnaires. The communications will be documented in the source worksheets. Remote visits would apply to any visit that could be conducted remotely without the subject being present, including remote programming, if available. Procedural visits (trial and IPG) and any unscheduled visits required for study-related adverse events would continue to be performed in office where possible.

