- Visit windows remain in place and should be maintained as much as possible. Subjects should be contacted via phone to collect AEs, medications and concurrent procedures. All questionnaires required at a visit should be obtained via phone, email or via mail based on site and/or subject preference.
- If by phone: site staff will read each question to the subject and record their answers. The site staff should initial and date the bottom of each form and indicate that it was completed via phone.
- If by email: the site staff should send the study questionnaires. Subjects can either print and manually complete or complete the forms electronically.
- If manually completed (printed): the subject will be instructed to initial and date each page and scan and email or mail the responses back to the site.
- If the forms are completed electronically: the subject will be instructed to complete the questionnaires and return the responses to the site as soon as possible, ideally, within 3 business days.

- If the questionnaires are sent in hard copy by mail: the subject should be instructed to complete the questionnaires and initial and date each page after completion and return to site as soon as possible. Ideally, within 3 business days of receipt.
- Source documentation should clearly describe the process utilized for each subject at each visit when these alternative methods are utilized.

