### **B.7.3. PRIMARY ENDPOINT**

Pain rating on the 10 cm Visual Analog Scale (VAS) is considered the primary outcome measure. VAS is the most widely used outcome measure in assessing pain due to its documented reliability and validity, ease in administration, and minimal training requirements for the administrator.

The primary effectiveness endpoint is the percentage of implanted subjects who respond to DTM SCS therapy at 3-months after device activation.

An Individual Responder is a subject that reports a decrease in upper limb pain VAS score by at least 50% at 3 months after activation of the permanent SCS system (Device Activation) as compared with Baseline measurement.

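### The 3-month responder rule makes no provision for other upper limb pain procedures, so relief from one can be counted as response to DTM

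*Combined protocol and SAP*

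**What the plan says.** B.7.3 defines response by the VAS change alone: "An Individual Responder is a subject that reports a decrease in upper limb pain VAS score by at least 50% at 3 months" after activation, relative to Baseline. It sets no condition on other treatment.

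The Baseline value is the score taken when eligibility is assessed. B.6.3 describes it as "average pain intensity (which will be used as Baseline pain intensity", and Table 1 places a VAS at Enrollment but none at the Baseline visit. Inclusion 3 requires that score to be at least 5 "out of 10 cm on the Visual Analog Scale (VAS) at enrollment".

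On procedures before enrollment, exclusion 9 (B.3.3, repeated in the Synopsis) reads "Has undergone, within 30 days prior to enrollment, an interventional procedure and/or surgery to treat upper limb pain, which is providing significant pain relief". Exclusion 16 adds "Any previous history of surgery on the posterior elements (laminectomy, posterior fusion) of the cervical spine".

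After enrollment, the limits on concurrent pain treatment concern medication. Inclusion 8 asks for compliance "including not increasing pain medications through the three months visit", and B.6.15 says that "Investigators/Study staff will instruct subjects not to change usage of any other concomitant pain medications". Procedures are mentioned once, as an item to gather in the remote-visit instructions of B.6.15: "Subjects should be contacted via phone to collect AEs, medications and concurrent procedures". They have no row in Table 1 and no rule in B.7 or B.9.2.

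**The concern.** With no control arm, the responder rate is a before-after figure. It can be attributed to DTM only so far as other causes of relief are kept out or accounted for. Medication is handled in some detail. Other procedures are not, and there are two ways in.

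- **After enrollment.** A subject may have an injection, block or operation for upper limb pain at any point up to the 3-month VAS. If pain has then fallen by half, the subject is a responder.
- **Before enrollment.** A candidate treated days earlier, with relief not yet present or with a temporary flare, passes exclusion 9 and enters with an unrelieved or raised Baseline. Later relief from that procedure counts toward the 40% trial threshold (B.6.1, B.6.6), which uses the same Baseline, and toward the 50% responder rule.

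In both cases the procedure can only help a subject reach the threshold, so the error in the reported rate is upward.

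**Working it through.** The plan has no figure to reproduce here. The 45 implanted subjects in B.5.4.1 are a judgement, with no hypothesis, effect size or precision target behind them. The check is a reading of the text followed by scenario arithmetic.

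**Does another provision close the gap?**
- Inclusion 3 (VAS of at least 5): met by a candidate whose recent procedure has not yet worked.
- Inclusion 7 (30 days of stable medication): does not reach a procedure that involves no medication change.
- Exclusion 16: posterior cervical surgery only.
- Pre-screening by a sponsor-designated physician (B.6.2): recent procedures may be seen, but no rule says what to do about them.
- B.7.1, which drops subjects with major deviations: nothing makes a pain procedure a deviation. Using the clause for this purpose would be an unplanned decision in an open-label study, possibly taken with outcomes known.

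**Time at risk.** The inputs are a trial of up to 10 days (B.6.5), up to 60 days to implant (B.6.7), up to 14 days to activation (B.6.8), and a visit at 3 months ±21 days (B.6.12). Three months is taken as 91 days.
- Longest, trial start to 3-month visit: 10 + 60 + 14 + 91 + 21 = 196 days. The interval from enrollment to trial start has no stated limit and comes on top.
- Shortest, activation to 3-month visit: 91 − 21 = 70 days.

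**Effect on the rate.** One subject is 1/45 = 2.2 points. For the expected shift, let *f* be the share of implanted subjects with such a procedure, *r* the responder rate without it, and *q* the share of would-be non-responders whom it turns into responders. Then

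shift = *f* × (1 − *r*) × *q*.

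The factor (1 − *r*) is needed because a subject who would respond anyway cannot be converted. All three values are assumptions.

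| *f* | *r* | *q* | Shift (points) | Subjects of 45 |
|---|---|---|---|---|
| 5% | 60% | 50% | 1.0 | 0.45 |
| 10% | 60% | 50% | 2.0 | 0.9 |
| 15% | 60% | 50% | 3.0 | 1.35 |
| 5% | 80% | 25% | 0.25 | 0.11 |
| 20% | 50% | 100% | 10.0 | 4.5 |

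The last two rows are the extremes for *f* from 5% to 20%, *r* from 50% to 80% and *q* from 25% to 100%.

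For scale, 27 responders of 45 (60%) has an exact 95% confidence interval of 44.3% to 74.3%.

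**The case against.** The case on the other side has real strength, and most of it limits how far the point can be pushed.

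- **Frequency is unknown.** A reader might infer that procedural relief *is* being scored as DTM response. No figure in the documents shows that any subject had such a procedure. Only *can be scored* is supported.
- **Exclusion 9 has a sensible purpose.** A reader might infer that its qualifier works backwards. But excluding people who are already relieved avoids a Baseline lowered by another treatment, and avoids implanting someone who is doing well. For a pre-enrollment procedure to affect the endpoint, its relief must also last to the 3-month visit, at least about 70 days after activation plus trial and implant time. A procedure shortly before that visit needs no such persistence, so the gap after enrollment matters more.
- **Medication control is wider than inclusion 8.** It would be wrong to say that subjects need only avoid an increase. B.6.15 also calls for Baseline doses to month 3 (with a reduction allowed in some cases), no fluctuation, and two weeks of stable dosing before visits. None of this touches procedures.
- **Recording at office visits cannot be judged.** The remote-visit text may mirror routine collection, and the case report forms are not available. What can be said is that Table 1 has no row for procedures and the analysis sections make no use of them.
- **The study is descriptive.** With no hypothesis there is no error rate to protect. That lowers the stakes but leaves the meaning of the primary percentage unclear.

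What stands is that the responder definition is silent on other procedures and no other section fills the gap.

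**Conclusion.** The point holds as a gap in the endpoint definition. As written, the plan allows relief from another upper limb pain procedure, whether new after enrollment or recent and not yet effective at enrollment, to be counted as response to DTM. For these cases the bias is upward, and a confidence interval would not reflect it.

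Its size cannot be obtained from the documents. Under the central assumptions (5% to 15% affected, a 60% responder rate otherwise, half of would-be non-responders converted) it is about +1 to +3 points, or roughly half a subject to one and a third. That is small beside the sampling uncertainty at 45.

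A reader might reach +2.5 to +7.5 points by supposing that half of *all* affected subjects become responders because of the procedure (5% × 0.5 and 15% × 0.5). That needs a responder rate without the procedure of 50% or less. At 60%, even full conversion of the rest gives at most 5% × 0.4 = 2 to 15% × 0.4 = 6 points.

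This is an inexpensive improvement to make before analysis. It does not show that the result is wrong, and no sample-size figure changes.

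**What to change.** 1. **B.7.3.** State that a subject who has an interventional procedure or operation for upper limb pain, other than implant or revision of the study system, between enrollment and the 3-month VAS counts as a non-responder in the primary analysis. Report the responder rate regardless of procedures as a sensitivity analysis.
2. **Table 1 and the case report form.** Add a row and a line to record such procedures at every visit, reaching back to 30 days before enrollment. Report the responder rate with and without subjects who had one in those 30 days.
3. **Optional, only if enrollment is still open.** Delete the relief qualifier from exclusion 9 in B.3.3 and the Synopsis. This is secondary. It closes the pre-enrollment gap only in part, since delayed relief can also follow a procedure on day 31. Revision 3.0 is dated about 15 months after first release, against 20 months of planned enrollment, so little recruitment may remain.

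**Cost.** Items 1 and 2 need a few sentences, one table row and one form line, with the approvals that E.6 requires for any change. The responder rate may be slightly less favourable. Some genuine DTM responders who had a minor procedure will be counted as failures, which the sensitivity analysis will show. Item 3 changes eligibility by amendment and makes a few candidates wait up to 30 days. Items 1 and 2 restrict no one's care; they settle in advance how the result is counted.

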## **B.4. TREATMENT GROUPS**

Subjects meeting the study eligibility criteria will be treated with DTM SCS programming approach. A trial period of up to ten days, which is the standard of care in SCS, will serve to determine if a subject is eligible to undergo permanent implantation of the SCS system.

## **B.5. STUDY DESIGN**

### **B.5.1. OVERALL DESIGN**

This is a post-market, prospective, open-label, observational, multi-center study designed to evaluate the effectiveness and to collect safety data of the DTM SCS programming approach in subjects with chronic, intractable pain of the upper limbs. Data at follow-up visits will be compared to baseline data collected at the beginning of the study.

### **B.5.2. BIAS MINIMIZATION**

This Clinical Study Plan and its associated documentation have been designed to minimize potential sources of bias. Each Investigator's qualification for meeting the requirements of this Clinical Study plan will be reviewed prior to their participation in this investigation.

### **B.5.3. BLINDING**

This open label, single-arm study is not blinded. All subjects eligible to participate will be trialed with commercially available Intellis trialing SCS system. Those who successfully trial DTM SCS programming may be implanted with a commercially available Intellis SCS system.

### **B.5.4. SAMPLE SIZE**

Primary Endpoint Assessment occurs at the 3-months follow up visit after activation of the implanted device. There is no statistical hypothesis to be evaluated in this study, but it is believed that approximately 45 subjects will be required to evaluate the effectiveness and to collect additional safety data of DTM SCS programming at the primary endpoint. Based on this requirement, the estimated sample size of this study is up to 90 consented subjects.,

#### **B.5.4.1 SAMPLE SIZE RATIONALE**

There is no statistical hypothesis to be evaluated in this study. It is believed that approximately 45 subjects permanently implanted subjects will be sufficient to evaluate the effectiveness and to collect additional safety data of the DTM SCS programming in the target population at the primary endpoint.

Up to 90 subjects will be consented to participate in the eligibility screening process. Those who do not meet all the inclusion criteria and none of the exclusion criteria will be considered screen failures and will not move into the trialing phase. It is estimated that approximately 55 subjects will be trialed. Only subjects with a successful trial phase will be eligible to move into permanent implantation of the device.

#### **B.5.5. STUDY DURATION**

The expected total duration of this study is approximately 26 months. Enrollment of subjects is expected to last 20 months. Subjects that have received the permanent implant will be followed up for 12 months after their device has been activated. A subject will likely be committed to the study for about 14 months. This consists of Baseline assessments, up to 10 days of trial stimulation, and 12 months of treatment following implantation and activation of the device. All current subjects or those who have completed their 6-month visit will be offered to return for an additional 12-month visit. This would increase their commitment to the study to 14 months

### **B.6. ENROLLMENT, ASSESSMENTS, AND CLINICAL PROCEDURE**

Enrollment of subjects will occur at the clinical sites after Institutional Review Board (IRB) approvals, and when written informed consent from subjects has been obtained. Prior to enrollment, Investigators and clinical site staff will approach subjects, who have been determined to be candidates for SCS therapy and talk about potential participation in the study. Following informed consent, the eligibility of subjects to participate in the study will be assessed according to inclusion and exclusion criteria outlined in this Clinical Study Plan. Various assessments including pain intensity, evaluation of medical history and records, and the Investigator's clinical judgment will be used in the selection process.

#### **B.6.1. SUMMARY OF STUDY PROTOCOL**

Potential study subjects will be identified from a pool of candidates for SCS therapy that are either affiliated with or referred to the clinical sites. Advertisements of the study may be used for recruitment purposes, upon approval of the patient recruitment materials by the study IRB(s). An informed consent form (ICF) will be given to the potential subject for private evaluation. The Investigator or Study Clinical Staff will be available to respond to

any questions the potential subject may have during evaluation of the ICF. Potential study subjects willing to participate in the study will visit the study site for providing written consent and for evaluation of eligibility to participate based on inclusion and exclusion criteria. Once a consented subject is deemed qualified to participate in the study, baseline assessments will occur followed by scheduling of the trial stimulation phase.

Subjects who complete a successful DTM SCS trial phase will be scheduled to receive a permanent implant of the SCS system and will undergo 3 months of therapy with assessments at 1, 3, 6 and 12 months after the activation of the implanted device. All current subjects or those who have completed their 6-month visit will be offered to return for an additional 12-month visit. This would increase their commitment to the study to 14 months. Baseline assessments will include measures for pain intensity, use of medication, and extent of disability.

Subjects will undergo a Trial Phase lasting up to 10 days to determine subject's response to DTM SCS. Commercially available stimulation leads and a commercially available external neurostimulator (ENS) will be used during the Trial Phase. Subjects will evaluate DTM SCS therapy based on pain intensity under optimal stimulation parameters within the specifications of the device. Subjects who have a "successful Trial Phase" (defined as a 40% or greater pain reduction from Baseline in their upper limb pain) will proceed to permanent implantation of a SCS system.

The implanted INS will be activated within 14 days after surgical procedure and SCS therapy will be evaluated for the next 12 months. Activation of the device marks the initial time point for effectiveness evaluation of the study therapy after implantation. Assessments of pain intensity, use of medication and study-related adverse events will be made through the 12 month following Device Activation. Additionally, a 3, 6 and 12months after Device Activation, subjects will also be assessed for extent of disability, Patient Global Impression of Change, subject satisfaction and paresthesia. All current subjects or those who have completed their 6-month visit will be offered to return for an additional 12-month visit. This would increase their commitment to the study to 14 months. Figure 1 summarizes the sequence of study-related assessments, procedures, and activities.

